7.4.2. Inclusion visit

The following data will be collected:

- Demographic: age, sex, size, weight, BMI, smoking, alcohol consumption, history of cirrhosis, diabetes or a chronic respiratory disease, heart failure;
- Reason for hospitalization:
 - Chronic respiratory disease decompensation : COPD, obesity hypoventilation, restrictive lung disease;
 - Acute severe asthma;
 - Community-acquired and hospital-acquired pneumonia;
 - ARDS;
 - Acute respiratory distress: infection, acute pulmonary edema, other identified causes, other non identified causes.
 - Pulmonary embolism;
 - Post-operative (urologic, digestive, vascular, and thoracic surgery);
 - Sepsis;
 - Coma;
 - Acute heart failure;
 - Multi-organ failure;
 - Cancer;
 - Continuous monitoring;
 - Other (detail).

- Medical diagnosis and medical treatment planned of hypoxemia (or cause of hypoxemia).

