 - When the findings from a chest CT-scan less than 12hours old are available;
 - For each clinical hypotheses;
 - For each level of certainty of clinical hypothesis;
 - For type of patients (reasons for admission the most represented);
 - For each research center.
2. Determine the level of agreement between the physiotherapist's diagnosis comparing the clinical vs LUS findings, overall, for the level of certainty of clinical diagnosis and for the population where a CT-scan is available;
3. Determine the frequency of changes in the chest physiotherapy following the assessment of the LUS results, overall and for each type of clinical hypothesis;
4. Determine the frequency of changes in the medical treatment (determined by intensivist) following the assessment of the LUS results performed by the physiotherapist, overall and for each type of clinical hypothesis.

4. Judgement criteria

4.1.Principal judgement criterion

Modification of the clinical decision: agreement (yes/no) between the lung and diaphragm US diagnosis and the clinical diagnosis and modification (yes/no) of the chest physiotherapy protocol, expressed using the Net Reclassification Index (NRI).

4.2.Secondary clinical decision-makingjudgementcriteria

1. Modification of the clinical decision:
 - When a chest CT-scan < 12h is available;
 - For each clinical hypotheses;
 - For the level of certainty of clinical hypotheses (Likert scale: strongly certain, certain, neither certain nor uncertain, uncertain, strongly uncertain);

- For type of patients (reasons for admission the most represented);
 - For each research center.
2. Proportion of agreement between clinical and LUS diagnosis:
- Overall;
 - For the level of certainty of clinical hypotheses (Likert scale: strongly certain, certain, neither certain nor uncertain, uncertain, strongly uncertain);
 - When chest CT-scan < 12h is available.
3. Proportion of cases when the chest physiotherapy protocol is modified following the results of the LUS:
- Overall;
 - For each type of clinical hypothesis;
 - When a chest CT-scan < 12h is available;
4. Modification of the clinical decision of intensivist:
- Overall;
 - For each type of clinical hypothesis;
 - When a chest CT-scan < 12h is available.

5. Inclusion/exclusion criteria:

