5.1. Inclusion criteria

Patients presenting the following criteria will be eligible:

- Hypoxemia ($SpO_2/FiO_2 < 315$ (15)) (indication for chest physiotherapy) (*cf. annexe 1*);
- Medical prescription for chest physiotherapy;
- First session of chest physiotherapy;
- Chest X-ray < 12h available;
- Physiotherapist/operator qualified in LUS available;
- Patient's consent.

5.2.Exclusion criteria

Patients presenting the following criteria will not be eligible:

[figure not shown]
- Presence of a contra-indication for chest physiotherapy;
- Absence of hypoxemia;
- Absence of a prescription for chest physiotherapy;
- Absence of a chest X-ray < 12h from the time of physiotherapy assessment;
- Physiotherapist/operator qualified in LUS not available;
- Lung and diaphragm US not possible (surgical emphysema, dressing, scarring, drains etc.);
- Refusal of the patient or a relative to participate in the study;
- Patients to be discharged on the day of the study;
- Patients in palliative care;
- Withdrawal/limitations of medical care with impending death.

6. Methodology:

6.1.Type of study

This is a multi-centre prospective (patients enrolled on admission) interventional study evaluating a routine assessment/treatment. The study intends to assess the impact of lung and diaphragm ultrasound on the usual physiotherapist's clinical decision-making process. Each included patient will be clinically assessed by a clinical physiotherapist, and then will have a lung and diaphragm ultrasound by another physiotherapist/operator blinded to the clinical assessment findings. The lung and diaphragm ultrasound findings will then be presented to both the intensivist and clinical physiotherapist to evaluate the impact on the independent clinical decision-making by both the intensivist and physiotherapist.

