7.4.5. LUS reporting to clinical physiotherapist and intensivist

The clinical physiotherapist and intensivist reviews the LUS report. Taking into account these LUS report, the clinical physiotherapist once again selects the chest physiotherapy treatment modalities indicated. The second chest physiotherapy treatment modalities will be recorded, with the reasons for a change of interventions (if indicated). The intensivist will again review any medical decisions that have been made. The new medical treatment for hypoxemia (or cause of hypoxemia) is recorded.

7.4.6. Second visit of the clinician physiotherapist: implementation of the chest physiotherapy treatment

After the review of the LUS report, the clinical physiotherapist may or may not decide to perform the chest physiotherapy treatment, to refer the patient to the intensivist, dependent upon his/her therapeutic strategy choice. The executed chest physiotherapy treatment provided will be recorded. The following data will be recorded:

- Current medical management:
 - o Oxygen therapy (and flow);
 - o Mechanical ventilation, NIV (PEEP, IPAP);
- Severity score: SOFA
- Vital signs: RR, HR, BP SpO₂, FiO₂ (true or estimated), body temperature, RASS, Glasgow coma score;
- Adverse effects during the chest physiotherapy treatment:
 - o Desaturation (< 4% of initial SpO₂);
 - o Decrease or increase of blood pressure (> 20% of initial SBP or DBP);
 - o Decrease or increase of heart rate (> 20% of initial heart rate);
 - o Endotracheal tube removal;
 - o Catheter or perfusion removal.

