7.4.8. Patient follow-up synthesis

	Pre-inclusion J 0	Inclusion J 0	First clinical physiotherapist visit J 0	LUS J 0	LUS results reading by the clinical physiotherapist and intensivist J 0	Second clinical physiotherapist visit J 0	End- research visit
Information consent	✓						
Demographic data		✓					
Reason for hospitalization, medical diagnosis if different		✓					
Medical management			✓			✓	
SAPSOFA , vital signs			✓			✓	
Medical diagnostic for respiratory condition		✓					
Medical treatment planned for respiratory condition		✓					
Clinical hypotheses of the clinical physiotherapist			✓		✓		
Choice of chest physiotherapy protocol			✓		✓		
LUS scan				✓			
LUS-scan report				✓	✓		
New choice of chest physiotherapy protocol						✓	
Adverse effect recording						✓	
New medical treatment planned for hypoxemia					✓		
ICU length of stay, duration of MV, vital status							✓

The data will then be entered in an e-CRF (Redcap.com) and analysed at the St. Joseph Hospital Network.

The statistical analysis will be conducted by the Clinical Research Centre (CRC) of the St. Joseph Hospital Network. An identifier will be attributed to each patient (initials of first name and family name – year of birth) and the data will be entered on an EXCEL file, which will be sent to the statistician in charge of the analysis at the St. Joseph Hospital Network.

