8.2.5. Modification of the intensivist clinical decision

Calculation of the net reclassification index (NRI):

$$\text{NRI (\%)} = (P_{\text{upevents-I}} - P_{\text{downevents-I}}) - (P_{\text{upnonevents-I}} - P_{\text{downnonevents-I}})$$

With:

Events: the results of the lung and diaphragm US are compatible with the medical diagnosis of intensivist for the patient respiratory condition for a clinical hypothesis.

Non Events: the results of the lung and diaphragm US are not compatible with the medical diagnosis of intensivist for the patient respiratory condition for a clinical hypothesis.

P_{upevents}: number of «events» when the LUS results modified the medical treatment for the patient respiratory condition divided by the total number of «events».

P_{downevents}: number of «events» when the LUS results didn't modify the medical treatment for the patient respiratory condition divided by the total number of «events».

P_{upnonevents}: number of «non-events» when the LUS results modified the medical treatment for the patient respiratory condition divided by the total number of «non-events».

P_{downnonevents}: number of «non-events» when the LUS results didn't modify the medical treatment for the patient respiratory condition divided by the total number of «non-events».

9. Justification for current care

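### The intensivist's plan is recorded at inclusion and not refreshed before the scan report, so same-day changes made for other reasons can be credited to ultrasound

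*Combined protocol and SAP*

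**What the plan says.** Secondary objective 4 (section 3.2) is to "Determine the frequency of changes in the medical treatment (determined by intensivist" after the ultrasound results are known, overall and by type of clinical hypothesis.

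The baseline for this is an item of the inclusion visit in 7.4.2: "Medical diagnosis and medical treatment planned of hypoxemia (or cause of hypoxemia". Section 6.1 describes the study as prospective, with "patients enrolled on admission". In the schedule (7.4.8), the row "Medical treatment planned for respiratory condition" has one tick, which falls under inclusion in the extracted table. The row "New medical treatment planned for hypoxemia" has one tick, which falls under the reading of the ultrasound results. The physiotherapist's examination (7.4.3) and the scan (7.4.4) come between the two.

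After the report, 7.4.5 says of the intensivist: "The new medical treatment for hypoxemia (or cause of hypoxemia) is recorded". Of the physiotherapist, the same section says the second choice is recorded "with the reasons for a change of interventions (if indicated".

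Section 8.2.5 then builds an NRI for the intensivist. Its numerators count cases "when the LUS results modified the medical treatment for the patient respiratory condition". Its events and non-events are defined by whether the scan agrees with the intensivist's diagnosis, which is also scheduled only at inclusion.

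**The concern.** A before-and-after comparison isolates the effect of the report only if the first record is taken just before the report is opened, or if each change comes with its reason. The physiotherapist's endpoint has both safeguards. The intensivist's has neither.

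A plan may change between inclusion and the report because a test result arrives or the patient's condition moves. The analyst would then hold two plans that differ and no stated cause. Section 8.2.5 wants only changes due to ultrasound but does not say who decides this, when, or from which data. At stake is the answer to secondary objective 4: how often a scan done by a physiotherapist changes medical treatment.

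**Working it through.** **1. The two clinicians side by side**

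| | Physiotherapist | Intensivist |
|---|---|---|
| Baseline | First physiotherapist visit, before the scan (7.4.3) | Inclusion visit (7.4.2, 7.4.8) |
| Steps between baseline and report | Scan | Physiotherapist's examination, then scan |
| Second record | After the report (7.4.5) | After the report (7.4.5) |
| Reason for change | Recorded (7.4.5) | Not asked for |

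The nearest substitute is the medical-management list in 7.4.3, taken before the scan. It covers drug classes, oxygen and ventilation already in place, not the intensivist's plan. The corresponding list after the report (7.4.6) is reduced to oxygen and ventilation.

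**2. Figures in the plan**

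There is none to reproduce for this endpoint. The expected NRI of 30% and the 150 patients in 8.1 concern the physiotherapist's decision. Only the 150 is used below, as a scale.

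**3. Effect on the frequency of change**

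Let m be the true proportion of plans changed by ultrasound and b the proportion changed for other reasons between the two records. Both are assumed values, taken as independent. If the two kinds of change cannot be told apart,

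observed = 1 - (1 - b)(1 - m).

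| True m | b = 5% | b = 10% | b = 20% |
|---|---|---|---|
| 0% | 5% | 10% | 20% |
| 10% | 14.5% | 19% | 28% |
| 20% | 24% | 28% | 36% |

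For example, m = 20% and b = 5% gives 1 - 0.95 × 0.80 = 0.24. With 150 patients and no ultrasound effect at all, the expected number recorded as changed would be 150 × 0.05 = 7.5, 150 × 0.10 = 15 or 150 × 0.20 = 30.

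**4. Effect on the NRI**

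In 8.2.5, within events and within non-events, the down proportion is one minus the up proportion. So

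NRI = (2P_up,events - 1) - (2P_up,nonevents - 1) = 2 × (P_up,events - P_up,nonevents).

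Take assumed true up proportions of 10% in events and 25% in non-events: NRI = 2 × (0.10 - 0.25) = -0.30.

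- Equal background of 10%: 2 × (0.19 - 0.325) = -0.27. Equal background of 20%: 2 × (0.28 - 0.40) = -0.24. The index shrinks by the factor (1 - b).
- Background 5% in events and 15% in non-events: 2 × (0.145 - 0.3625) = -0.435. The index moves away from zero.
- The same unequal background with no ultrasound effect: 2 × (0.05 - 0.15) = -0.20. An index appears where the truth is 0.

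Unequal backgrounds are plausible because the diagnosis that defines events also dates from inclusion. A diagnosis later revised for other reasons could put the patient among the non-events and change the plan as well.

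**The case against.** The strongest defence has four parts.

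- *Section 8.2.5 does not count every difference.* A reader might infer that any discrepancy between the two records is scored as ultrasound impact. The text does not say so: it counts changes made by the ultrasound results. Section 7.4.5 also has the intensivist reconsider decisions already taken, which could include those standing when the report is read. This stands. What is missing is a way to apply the definition, so unrelated changes can be credited to ultrasound; it is not established that they will be.
- *The interval may be short.* Every decision step is on day 0 and participation lasts one day. Eligibility requires an available ultrasound operator and a chest X-ray less than 12 hours old, which ties inclusion to the assessment. Describing the window as the first hours in the ICU goes further than the documents: patients may also be identified during the day, and one recruiting unit is a post-ICU rehabilitation unit. This stands, but no section limits or records the interval.
- *Referral by the physiotherapist is not shown to intervene.* Referral to the intensivist can be chosen before the scan (6.5.1.5), so a reader might infer that it alters the medical plan before the report. Section 7.4.6 places the decision to refer after the report has been reviewed, and 6.1 calls the two clinicians' decisions independent. Nothing rules out earlier contact, but the documents do not support naming it as a source of bias.
- *Upward bias does not carry over to the NRI.* This is right: with equal backgrounds the index moves toward zero.

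The case report form is not among the annexes, so it may hold an attribution field that cannot be seen here. If so, the protocol should describe it and 8.2.5 should use it.

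**Conclusion.** The point holds as a gap in attribution for one secondary objective. The intensivist's diagnosis and plan are recorded at inclusion and not refreshed before the report, and the protocol asks for no reason for change. Changes due to ultrasound therefore cannot be separated from other same-day changes.

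The frequency in objective 4 can only be inflated by this: by 4 to 16 percentage points at a true 20%, and by 4.5 to 18 points at a true 10%, for an assumed background of 5-20%. These sizes rest on the assumed rates, on independence, and on no attribution being made; a short interval would bring them close to zero. For the NRI neither the size nor the direction of bias can be stated in advance.

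The primary endpoint is not touched, because the physiotherapist's choice is recorded before the scan.

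**What to change.** 1. In 7.4.5 and the schedule, have the intensivist confirm or update the diagnosis and planned treatment immediately before the report is opened, with the time. Use this record in 8.2.5 both as the treatment baseline and to define events and non-events.
2. After the report, record the intensivist's reason for any change, as 7.4.5 already does for the physiotherapist. State in 8.2.5 that a change counts as due to ultrasound only on that basis.
3. Add to 8.2.5 the proportion of patients whose medical treatment changed because of ultrasound, with a 95% CI, overall and by clinical hypothesis. Objective 4 asks for a frequency, and 8.2.5 gives only an NRI.

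The cost is a few case report form fields and a short extra step for the intensivist before the report is read.

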7.4.3. Initial clinical physiotherapist visit

The clinical physiotherapist undertakes the patient clinical examination, reviews the chest x-rays and additional tests as available. Moreover, he/she reviews the CT-scan if performed < 12h at the patient's admission including the radiology report. Following the clinical examination, the clinical physiotherapist formulates his/her clinical hypotheses. Among this formulated clinical hypotheses, the physiotherapist chooses a primary clinical hypotheses (the choice is left to the discretion of the clinical physiotherapist, based on the probability and priority of the clinical hypothesis in term of treatment). The primary clinical hypothesis and the secondary clinical hypotheses (if adapted) will be recorded in the case report form (CRF). According the primary clinical hypothesis, the clinical physiotherapist records his chest physiotherapy treatment modalities in the CRF.

The following data will be recorded:

- Medical management:
 - o Hypnotics ~~(and dose)~~;
 - o Opiates ~~(and dose)~~;
 - o Steroids ~~(and dose)~~;
 - o Anti-hypertensives ~~(and dose)~~;
 - o Antibiotics ~~(and dose)~~;
 - o Oxygen therapy (and flow);
 - o Mechanical ventilation, NIV (PEEP, IPAP, O₂ dose);
 - o Tracheotomy;
- Severity score: SAPSOFA
- Vital signs: RR, HR, BP SpO₂, FiO₂ (true or estimated), body temperature, RASS, Glasgow coma score;
- Clinical hypotheses of the clinical physiotherapist;
- Choice of chest physiotherapy protocol (before LUS).

7.4.4. Ultrasound physiotherapist/operator visit

Following the clinical physiotherapist visit, the ultrasound physiotherapist/operator performs a lung and diaphragm ultrasound. He is blinded to the patient's status and clinical physiotherapist examination. He/she is not involved in patient management or patient clinical decision-making. The ultrasound findings are recorded in the LUS report (*cfannexe4*). The LUS report is reported to the clinical physiotherapist and to the intensivist. The ultrasound diagnosis(es) is recorded.

7.4.5. LUS reporting to clinical physiotherapist and intensivist

The clinical physiotherapist and intensivist reviews the LUS report. Taking into account these LUS report, the clinical physiotherapist once again selects the chest physiotherapy treatment modalities indicated. The second chest physiotherapy treatment modalities will be recorded, with the reasons for a change of interventions (if indicated). The intensivist will again review any medical decisions that have been made. The new medical treatment for hypoxemia (or cause of hypoxemia) is recorded.

7.4.6. Second visit of the clinician physiotherapist: implementation of the chest physiotherapy treatment

After the review of the LUS report, the clinical physiotherapist may or may not decide to perform the chest physiotherapy treatment, to refer the patient to the intensivist, dependent upon his/her therapeutic strategy choice. The executed chest physiotherapy treatment provided will be recorded. The following data will be recorded:

- Current medical management:
 - o Oxygen therapy (and flow);
 - o Mechanical ventilation, NIV (PEEP, IPAP);
- Severity score: SOFA
- Vital signs: RR, HR, BP SpO₂, FiO₂ (true or estimated), body temperature, RASS, Glasgow coma score;
- Adverse effects during the chest physiotherapy treatment:
 - o Desaturation (< 4% of initial SpO₂);
 - o Decrease or increase of blood pressure (> 20% of initial SBP or DBP);
 - o Decrease or increase of heart rate (> 20% of initial heart rate);
 - o Endotracheal tube removal;
 - o Catheter or perfusion removal.

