6.5.1.5. Choice of chest physiotherapy treatment

The clinical physiotherapist will define the chest physiotherapy treatment modalities according to the formulated clinical hypothesis. The following treatments may be proposed :

- No chest physiotherapy treatment indicated;
- Refer to the intensivist;
- Non-invasive ventilation;
- CPAP (if non-ventilated patient) or PEEP modifications (if ventilated patient);
- Manual or ventilator hyperinflation;
- Mechanical in-exsufflator (Cough Assist ©);
- Rib cage compressions, manual assisted cough;
- Endo or naso-tracheal suctioning;
- Positioning;

- Semirecumbent position (head 45° from bed);
- Laterocubitus;
- Early mobilization:
 - Sitting on side of bed;
 - Standing;
 - Sitting on chair.

The choice of treatment according to the clinical hypothesis is defined in annexe 2b. The clinical physiotherapist will define the chest physiotherapy treatment modalities for the primary clinical hypothesis. The chest physiotherapy treatment modalities will be defined both before and again separately after the LUS and Diaphragm US examination.

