6.5.2.4. Lung and diaphragm ultrasound report

The physiotherapist/operator will write a detailed LUS-scan report, which will be given to the clinical physiotherapist. When LUS is performed by a french physiotherapist, the LUS report will be checked and validated by the referent intensiviste.-The LUS-scan report# will include the LUS and Diaphragm diagnosis and describe the signs observed in the different regions of the chest (*cf. annexe4*). The clinical physiotherapist is trained to interpret LUS reports. The clinical physiotherapist then determines the options or changes to treatment based on the US findings.

7. Studyprogress

7.1.Study planning

- Ethic comittee submission: December 2016;
- Study comencement: January 2016;
- Inclusion duration : 12 months;
- Length of patient participation: one day;
- End of inclusion: January 2017;
- Total duration of the study: 18 months;
- Congress communications: French Intensive Care Society Congress, ESICM, ERS, ATS, from April 2018;
- Publication: September 2018;
- Target journal: Physical therapy, Intensive Care Medicine or Critical Care Medicine.

7.2.Recruitment method

Patients will be recruited in the Surgical ICU of the CHU de Dijon, Medical-Surgical ICU of Paris St. Joseph's Hospital, Respiratory ICU and Post-ICU Rehabilitation Unit of Forcilles' Hopital and the ICU of St Vincent's Hospital.

Patients admitted to the ICU and who meet the inclusion criteria will be invited to take part in the study. Patients with hypoxemia will be identified by the duty physician at the time of

transfer to the unit or by the principal investigator and the coordinating investigator during the day. Written informed consent will be collected (*cf. annexes 5a and 5b*).

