8.2.3. Agreement between clinical and LUS diagnosis

Calculation of Kappa index:

The clinical diagnosis and the lung ultrasound allow to diagnose the following events : (the retained airway secretions and bronchospasm diagnoses aren't included in the analysis as LUS doesn't allow their diagnosis (LUS may only be compatible with these hypotheses):

- T1: pneumonia/consolidation;
- T2: atelectasis (~~passive or active mechanism~~ obstructive);
- T3: pleural effusion;
- T4: pulmonary edema or global interstitial syndrome;
- T5: pneumothorax;
- T6: reduced aeration at the most dependent parts of the lungs;
- T7: diaphragm dysfunction (unilateral or bilateral);
- T8: examination is inconclusive.

Contingency table:

		Lung ultrasound								Total
		T1	T2	T3	T4	T5	T6	T7	T8	
Clinical diagnosis	T1									
	T2									
	T3									
	T4									
	T5									
	T6									
	T7									
	T8									
Total										

Proportion of observed agreement:

$$P_a = \frac{1}{n} \sum_{i=1}^p n_{ii}$$

Theoretical proportion of observed agreement:

$$P_e = \frac{1}{n^2} \sum_{i=1}^p n_{i.} \cdot n_{.i}$$

Kappa :

$$\kappa = \frac{P_a - P_e}{1 - P_e}$$

The Kappa index will be calculated for the global population, the population where the clinical diagnosis is « strongly certain/certain » and « strongly uncertain/uncertain » and the population with a CT-scan < 12h.

8.2.4. Proportion of cases when the chest physiotherapy protocol is modified following the results of the LUS:

Calculation of proportion: $P_{\text{upevents}} + P_{\text{upnonevents}}$ for all of the clinical hypothesis, for each clinical hypothesis and in the CT-scan <12h subpopulation.

With a confidence interval at $\alpha=0.05$.

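### No second decision without ultrasound is observed, so the modification proportion cannot be ascribed wholly to the scan, and the effect on the primary NRI has no fixed direction

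*Combined protocol and SAP*

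**What the plan says.** Section 6.1 describes a single group: "Each included patient will be clinically assessed by a clinical physiotherapist, and then will have a lung and diaphragm ultrasound by another physiotherapist/operator". Under section 6.5.1.5 the treatment modalities "will be defined both before and again separately after the LUS and Diaphragm US examination". The order of events is fixed in section 7.4.4: "Following the clinical physiotherapist visit, the ultrasound physiotherapist/operator performs a lung and diaphragm ultrasound". In section 7.4.5 the report goes to the same clinician, and "the clinical physiotherapist once again selects the chest physiotherapy treatment modalities indicated". That section also asks for the reasons when the treatment changes.

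On timing, section 7.1 gives "Length of patient participation: one day", and the table in section 7.4.8 places every step from pre-inclusion to the second physiotherapist visit on day 0. The published text sets no maximum gap between the two plans and lists no clock time as a data item. Chest X-ray and CT, by contrast, carry a 12-hour limit.

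Section 8.2.4 estimates the "Proportion of cases when the chest physiotherapy protocol is modified following the results of the LUS". Section 8.2.1 uses the same modifications, split by whether the ultrasound is compatible with the clinical diagnosis, to form the primary NRI. None of sections 8.2.1 to 8.2.5 has a term for background change or uses the recorded reasons.

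**The concern.** A clinician asked twice for a plan may answer differently the second time, because of reconsideration or because the patient has changed. Here the only second answer available is one given with the report in hand, so the two sources of change cannot be separated.

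Some wait is built in. A different operator must scan the patient. At the French sites a referent intensivist must also be present and must validate the report (sections 6.5.2.2 and 6.5.2.4). The length of the wait is not captured.

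At stake is the reading of secondary objective 3, and to a less predictable degree the primary index. The study calls itself a pilot with no prior information on modification rates (section 8.1), and a positive result is meant to lead to a randomised trial (section 10).

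**Working it through.** **Inputs.** From section 8.1: 150 patients, at least 50 modifications, expected NRI 30%. From section 8.2.1: the NRI formula and test. The background change rate b is in no document; I assume 5%, 10% and 15%.

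**The plan's own figure.** 50/150 = 1/3, so the target implies that one third of plans change. The stated 30% would give 50/0.30 = 166.7, that is 167 patients, or 150 × 0.30 = 45 modifications. The 150 is reproduced only with a rate of one third, so I use one third below. That mismatch is a separate matter.

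**Modification proportion.** Let p be the scan-related rate, independent of b. Then observed = 1 − (1 − p)(1 − b). With observed = 1/3, p = 1 − (2/3)/(1 − b).

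| b | p | Overstatement (points) | Patients of 150 |
|---|---|---|---|
| 5% | 29.8% | 3.5 | 5.3 |
| 10% | 25.9% | 7.4 | 11.1 |
| 15% | 21.6% | 11.8 | 17.6 |

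This takes the proportion as modified plans over all patients. Section 8.2.4 as written adds two stratum proportions with different denominators. With no scan effect and equal b, that sum would be 2b, or 10% to 30%.

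**Primary NRI.** In each stratum a plan is either modified or not, so P_up + P_down = 1. The formula reduces to NRI = 2(P_up,events − P_up,nonevents).

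- *Equal b in both strata.* Each P_up becomes P_up + b(1 − P_up), so the difference is multiplied by (1 − b). With no scan effect the NRI stays at 0. A true absolute NRI of 0.30 becomes 0.285, 0.27 and 0.255 at b = 5%, 10% and 15%.
- *Unequal b, no scan effect.* The absolute NRI is twice the difference. For 5% in compatible and 15% in incompatible cases it is 2 × 0.10 = 0.20. For 5% and 20% it is 0.30, the whole expected value. Under the definitions in 8.2.1 the sign would be negative.
- *Effect on the test.* Because P_up + P_down = 1, the planned standard error is √(1/events + 1/nonevents). For an assumed 75/75 split it is 0.163, giving z = 1.22 and 1.84, both below 1.96. At this size the distortion falls mainly on the estimate.

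**Precision of a measured b.** In 150 patients, a rate of 10% has a 95% half-width of 1.96 × √(0.10 × 0.90/150) = 4.8 points.

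**The case against.** The best defence is that the plan already limits the problem. Section 8.2.1 counts cases where the ultrasound results changed the treatment, not any difference between plans, and section 7.4.5 collects reasons. All decision steps fall on one day, no new physiotherapy examination is scheduled between the two plans, and Annexe 2b ties modalities to hypotheses. Patient status is measured again at the second physiotherapist visit (section 7.4.6: "Vital signs: RR, HR, BP SpO₂, FiO₂ (true or estimated), body temperature, RASS, Glasgow coma score"). The study is a pilot, with a randomised comparison to follow.

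Much of this stands, and it rules out the strongest reading. A reader might infer that all background change is credited to the scan. The documents do not support that, since a change with another stated reason could be set aside. But no rule does so, and the reasons come from an unblinded decision-maker after reading the report. The repeat measurements come after the re-selection and enter no analysis. Annexe 2b narrows the choice without fixing it, because the primary hypothesis is left to the physiotherapist's discretion (section 6.5.1.4). The table in section 7.4.8 shows later entries for the treatment choice, but all fall at or after the reading of the report.

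A reader might also set 150 × 5% to 15% = 7.5 to 22.5 background changes against the target of 50 and call 15% to 45% of it spurious. That ignores plans that would change for both reasons. Allowing for overlap, the excess is 5.3 to 17.6 patients, about 11% to 35% of 50.

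**Conclusion.** The point holds in limited form. The modification proportion in 8.2.4 cannot be ascribed wholly to the scan. At an assumed background rate of 5% to 15%, a total of one third and independence of the two sources, it overstates the scan-related rate by 3.5 to 11.8 points. A different true background rate would change these figures.

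It may be tempting to conclude that the primary result is biased upward. The plan's own formula does not support that: background change common to both strata cannot inflate the NRI. Inflation requires more background change where the ultrasound is incompatible. That is plausible if uncertain cases are both more often incompatible and more often reconsidered, but nothing in the documents shows it. The direction for the NRI is therefore unknown. This is a cheap improvement to make, not a defect that invalidates the design.

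**What to change.** - In section 7.4.5, immediately before the report is opened, have the clinical physiotherapist re-confirm or re-enter the hypothesis and modalities, with the clock time. Use this plan as the 'before' value in 8.2.1 and 8.2.4.
- Report the change from the 7.4.3 plan to the re-entered plan separately, with a 95% interval, as a probable lower bound on background change. Do not also subtract it from the re-baselined rate, because that would remove change during the wait twice.
- In 8.2.4, pre-specify a second count limited to modifications whose recorded reason names an ultrasound finding. This needs no new data.

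The cost is one CRF line, a clock time and about a minute per patient. The re-entry may be anchored on the first plan, which is why its change rate is only a probable lower bound. The reported modification figure will probably be lower.
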